11.0 STATISTICAL CONSIDERATIONS

11.1 Study Overview

This is a randomized phase III clinical trial to determine the efficacy of early palliative care vs. standard oncology care on patient and family caregiver reported outcomes, quality of EOL care and resource utilization in newly diagnosed incurable lung or non-colorectal gastrointestinal cancer. This trial implements a group sequential design without interim analysis.

11.2 Sample Size, Accrual Time, and Study Duration

11.2.1 Sample Size

A 4-5 point change in the FACT is considered a clinically meaningful change (CMC) and was the difference detected between arms in our previous study.⁶⁵ Enrolling 140 patients per study arm will provide 80% power to detect at least a 4-point change from baseline to week 12 (standard deviation was 11.87 from the pilot study) between arms using a two-sided two-sample *t*-test with at 5% significance level.

Based on our previous palliative care study, the rate of missing data for primary endpoint patient-reported measures was approximately 20-30%. We will therefore increase our sample size to 200 patients per arm to ensure a sufficiently large margin to have adequate power to detect the CMC. Based upon our current study enrollment rates, we estimate that with 400 patients, approximately 300 family caregivers will also enroll.

11.2.2 Accrual Rate and Accrual Duration

We anticipate being able to accrue approximately 20 patients per month based on our best estimate for this new area of research. Using this estimate, we would complete accrual within 20 months and data maturation within 26 months from study initiation.

11.2.3 Primary Endpoint Completion Date for ClinicalTrials.gov Reporting

For purposes of ClinicalTrials.gov reporting, the Primary Endpoint Completion Date (PECD) for this study is the time the last patient registered has been followed for at least 12 weeks.

11.3 Statistical Design and Analysis for the Primary Endpoint

11.3.1 Primary Endpoint

The total scores of FACT-G will be calculated using the accompanying scoring algorithms. They will be further converted into a 0-100 quality of life scale for standardization. Change in FACT-G scores from baseline to 12 weeks between study arms will be the primary endpoint for this study. The disease-specific questions (additional concern) of FACT-L, FACT-E or FACT-Hep will be summarized in a descriptive manner between study arms.

11.3.2 Analysis Plan

A modified intent-to-treat principle³⁸ will be applied for statistical analysis of efficacy in evaluable patients. Evaluable patients are defined as all patients meeting the eligibility criteria who did not cancel prior to receiving intervention.

The primary analysis is to compare the change in FACT score from baseline to 12 weeks between study arms. We will perform preliminary analyses to examine how much QOL data are likely missing at random (MAR) or missing not at random (MNAR). However, missing data are expected to be MNAR as patients with poor QOL tend to have lower chances of completing a questionnaire, especially immediately prior to death.⁶⁶ We will examine the

pattern of missing data by comparing average scores among patient subsets defined by their available data and survival status. We will then use the pattern mixture models^{67,68} to adjust for MNAR bias by stratification based on survival data. We will compare study arms overall by weighting the within-stratum estimates with the estimated probability of being in each distinct combination of intervention arm and survival duration.

Sensitivity analysis will be conducted by exploring imputation method such as the last-observation carried forward, and the worst rank score analysis⁶⁹, favoring the more conservative method.

In the pattern mixture model, repeated measures of FACT will all be included in the repeated measures model to estimate the change from baseline to 12 weeks for primary analysis. Selected demographic and clinical factors (including stratification factors) may be incorporated when examining change in QOL scores across the four time points (baseline, 6, 12, and 24 weeks).

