7.0 INTERVENTION

During registration, patients will be randomized to receive either early palliative care (Arm 1) or standard oncology care (Arm 2).

Over the course of the study patients and their family caregivers in both arms will be asked to complete questionnaires about quality-of-life, mood, and their perception of prognosis and treatment goals during regularly scheduled oncology clinical visits at baseline and week 6, 12, and 24 visits.

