7.1 Early Palliative Care Arm

The intervention will be comprised of one baseline visit and palliative care visits or phone calls (if a clinic visit is not feasible) at least every four weeks throughout the patient's life.

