7.1.1 Day of Registration

- Patient and family caregiver will be asked to complete baseline self-report questionnaires. See Appendices II and III, respectively, for questionnaires.

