7.1.2 Subsequent Medical Oncology/Infusion Visits

- A PC clinician will meet with patients randomized to early PC within one month of registration. This should be done at the patient's next medical oncology or infusion visit following registration.
- The PC clinician will meet with patients and family caregivers (if present at the appointments) at a minimum of every four weeks in the outpatient care setting (oncology clinic or infusion suite). PC visits will be coordinated with regularly scheduled cancer center appointments to reduce burden of multiple hospital visits.
- If patients are unable to come to the clinic for a scheduled PC visit, at least one attempt will be made to reschedule the visit within seven days of the scheduled PC visit. If a rescheduled in-person visit is not feasible, the PC clinician will conduct the visit over the telephone and document the content and nature of the visit in the medical record. Clinic visits are strongly preferred to telephone visits and should be attempted as much as possible.
- Patients, family caregivers, or the PC team may initiate consultations as needed.
- PC clinicians should follow the guidelines as detailed in Appendix I.
- Depending on clinic space, workflow, and patient preference, PC clinicians may see patients in the clinic or in the chemotherapy infusion room.
- If a patient is admitted to the hospital during the study period, they should be seen at least once by either their outpatient palliative care clinician or the inpatient palliative care hospital based team. Additional follow up during the hospital admission is not dictated by the study requirements and patients should be followed as per their institution practice.

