7.2 Standard Oncology Arm

The standard oncology treatment will consist of questionnaire assessment only as outlined below.

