7.2.2 Subsequent Medical Oncology/Infusion Visits

After patients and family caregivers have been enrolled, the patient will meet with the treating oncologist(s) for the patient's standard treatment visit activities without the scheduled study intervention of palliative care.

Patients and family caregivers may consult with PC clinicians at their request or at the discretion of their treating oncologist. In such instances, individual PC clinicians will follow standard oncology participants per their clinical judgment, rather than according to the required time intervals for study patients receiving the early palliative care intervention.

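### The primary analysis set lets randomized patients drop out through a cancellation rule with no defined event, after their arm is known, and no all-randomized analysis is named

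*Combined protocol and SAP*

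**What the plan says.** Section 11.3.2 applies a modified intent-to-treat principle to evaluable patients: "Evaluable patients are defined as all patients meeting the eligibility criteria who did not cancel prior to receiving intervention". It defines neither term. The reference cited there for the principle (number 38) is listed in section 13.0 as a matched cohort study of hospice use and surviving spouses. Judged by that title, it supplies no definition.

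The timing comes from section 7:

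- Section 7.0 places randomization within registration.
- On the day of registration, sections 7.1.1 and 7.2.1 give both arms the same step: "Patient and family caregiver will be asked to complete baseline self-report questionnaires".
- For the early PC arm, section 7.1.2 says "A PC clinician will meet with patients randomized to early PC within one month of registration", and adds "This should be done at the patient's next medical oncology or infusion visit following registration".
- For the standard arm, section 7.2 says "The standard oncology treatment will consist of questionnaire assessment only as outlined below". Section 7.2.2 describes its oncology visits as taking place "without the scheduled study intervention of palliative care".

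Section 10.2 deals with early withdrawal. It does not speak of cancelling and does not link withdrawal to the analysis set. The sensitivity analyses named in 11.3.2 are last observation carried forward and worst-rank scoring. No analysis of all randomized patients appears in section 11.

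**The concern.** The rule operates after randomization in a trial for which no masking is described. A patient who learns the assignment and then cancels can be removed from the comparison that randomization was meant to protect. If the reason for cancelling is related both to the arm and to later quality of life, the retained groups are no longer comparable. The pattern-mixture model cannot repair this, because it is fitted only to patients still in the set.

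The missing definitions add a second problem, since two analysts could apply the sentence differently and obtain different sets. The protocol mostly uses the word intervention for palliative care (sections 1.5 and 7.2.2). On that reading the PC-arm window can stay open for up to a month, and the standard arm has no event that closes it.

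The primary test also matters beyond itself. Under the gatekeeping procedure in 11.4.2, its result decides whether the caregiver and end-of-life analyses are tested formally.

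**Working it through.** **The plan's own figure.** Section 11.2.1 gives a 4-point difference, SD 11.87, two-sided 5%, and 140 per arm for 80% power. SE = 11.87 × √(2/140) = 1.419, and 4/1.419 = 2.82. Power = Φ(2.82 − 1.96) = 80.5% by the normal approximation, or 80.2% by the noncentral t. The figure reproduces. With 200 enrolled per arm, 30% missing leaves 140 scored and 20% missing leaves 160.

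**Bias illustration.** The documents give no cancellation rate and no outcome difference, so every input except the SD and the 140 is an assumption.

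- x = share of the PC arm excluded, with none excluded in the standard arm: 2%, 5%, 10%.
- g = gap in 12-week change between excluded and retained patients: 4 points, 8 points, or 11.87 points (one SD).
- Bias if all those excluded could have given a 12-week score = x × g.
- If only half could, the part due to the rule = x × g / 2. The rest would be missing under any analysis set.
- SE = 11.87 × √(1/(140(1 − x)) + 1/140) = 1.426, 1.437, 1.458 at x = 2, 5, 10%.
- Type I error = P(|Z + bias/SE| > 1.96).

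| x | g | Bias, all scored | Type I | Bias, half scored | Type I |
|---|---|---|---|---|---|
| 2% | 4 | 0.08 | 5.0% | 0.04 | 5.0% |
| 2% | 11.87 | 0.24 | 5.3% | 0.12 | 5.1% |
| 5% | 8 | 0.40 | 5.9% | 0.20 | 5.2% |
| 5% | 11.87 | 0.59 | 7.0% | 0.30 | 5.5% |
| 10% | 4 | 0.40 | 5.9% | 0.20 | 5.2% |
| 10% | 8 | 0.80 | 8.5% | 0.40 | 5.9% |
| 10% | 11.87 | 1.19 | 12.9% | 0.59 | 6.9% |

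With equal exclusion in both arms and comparable excluded patients, the bias is 0 and the type I error stays at 5.0%.

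If the sign runs against PC, the effect is lost power. Take a true 4-point effect and half scored. At the mild end, (4 − 0.04)/1.426 = 2.78, so power = Φ(2.78 − 1.96) = 79.3%. At the extreme, (4 − 0.594)/1.458 = 2.34, so power = 64.7%.

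**Cost of restoring the excluded patients.** Assume the restored PC-arm patients are all scored and gain nothing from assignment to PC. The effect becomes 4(1 − x), with n scored per arm. The right comparator is the evaluable set, which has n(1 − x) scored in the PC arm and the full 4-point effect.

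| Restored | Diluted effect | n = 140: evaluable → all randomized | n = 160: evaluable → all randomized |
|---|---|---|---|
| 3% | 3.88 | 79.9% → 78.1% | 84.9% → 83.2% |
| 5% | 3.80 | 79.5% → 76.4% | 84.5% → 81.7% |
| 10% | 3.60 | 78.4% → 71.8% | 83.5% → 77.4% |

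Both sets of figures use a simple two-sample comparison by the normal approximation. The planned repeated-measures pattern-mixture model would give somewhat different values.

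**The case against.** The strongest reply is that this is a gap in definition with no demonstrated harm. Modified intent-to-treat sets of this kind can be harmless when few patients cancel. At 2% excluded, the bias is at most 0.24 points even if every canceller is scored. A patient who cancels within a month may have baseline data only and would be missing at week 12 under any set. Section 10.2 already asks patients who prefer to stop PC visits whether they will go on completing questionnaires, although it does not expressly cover those who decline before the first visit. All of this stands, and it limits the size of the point.

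Two stronger readings are tempting.

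- A reader might infer that exclusion must differ by arm. The documents do not establish this. A common start at the baseline step or at the next oncology visit would be near neutral. Both arms' content sits under the section 7.0 heading on intervention, and both share the same day-of-registration questionnaires. For the same reason, it is not clear that the standard-arm window closes at baseline while the PC-arm window stays open. The text selects none of these readings.
- A reader might infer that the bias favours PC, or take 12.9% as the expected type I error. The direction is unknown. The 12.9% needs 10% cancellation in the PC arm only, a gap of a full SD, and a 12-week score from every canceller.

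The reply does not remove the core. The sentence permits exclusion after the arm is known, and no planned analysis would show whether that changed the result.

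**Conclusion.** The point holds in a limited form. It is certain from the text that the rule permits exclusion after randomization, that neither term is tied to an event in either arm, and that no all-randomized analysis is named. That exclusion would in fact differ by arm is plausible, because of how the protocol mostly uses the word intervention, but it is not established.

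The size and direction of any bias are unknown. Under the stated assumptions, with half of those excluded able to give a score, it is 0.04-0.59 points against the 4-point target, with a type I error of 5.0-6.9%. The upper bound with all scored is 1.19 points and 12.9%. The bias is negligible if few cancel or if an arm-neutral reading is applied. The change is worth making because it is cheap and because the definition should not be settled after cancellations have been seen by arm.

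**What to change.** In section 11.3.2:

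1. Make the primary analysis set all randomized patients, analysed as assigned. The only exception is patients found ineligible on pre-randomization data, judged without regard to arm.
2. Handle missing 12-week scores in that set with the planned pattern-mixture model.
3. Keep the evaluable set as a sensitivity analysis. Define cancelling, and name one cut-off event that applies equally to both arms.
4. Report exclusions by arm, with timing and reason.

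The cost in text is a few sentences. The statistical cost is possible dilution if the restored PC-arm patients gain no benefit. Power for a 4-point effect then falls by about 2 to 7 percentage points at 3-10% restored with 140 scored per arm (79.9% to 78.1% at 3%, 78.4% to 71.8% at 10%). The falls are slightly smaller with 160 scored. The sample size can stay at 200 per arm, but the power statement in 11.2.1 should carry this caveat. Restored patients who give no 12-week score would still depend on the missing-data model, so the change reduces the exposure without removing it entirely.

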1.4 Study Design

This study will be a randomized, controlled trial of early PC integrated with standard oncology care versus standard oncology care alone. Patients will be randomized in a 1:1 fashion between study arms. The dynamic allocation procedure was adopted to balance the marginal distributions of stratification: tumor type (lung vs. esophageal/gastric vs. hepatic/biliary/pancreatic/ unknown primary), and family caregiver participation (yes vs. no).⁵⁶ We modeled this study design to be identical to the completed and ongoing trial at the Massachusetts General Hospital (MGH) Cancer Center. We are not randomizing by site (i.e. cluster-randomized design) due to several reasons: (1) Although such a design would reduce contamination effects, it introduces site effects that could also impact outcomes; (2) In both of our prior trials, there was minimal contamination with few patients in the standard care arm referred for PC in the outpatient care setting; and (3) Within Alliance, ensuring equivalent sites across geographical regions with the same PC resources would be challenging. We have also decided not to include an attention control group as the logistical and sample size requirements for a third study arm would be substantial. Additionally, the observed clinical benefits of PC in our previous investigation did not appear to be merely due to increased clinician time with patients and families but related to the expertise of PC clinicians. We anticipate including approximately 20 Alliance sites with a minimum of 10 community sites with an enrollment goal of at least 15 patients per site.

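### LOCF does not stress the informative missingness that the plan itself expects, and preferring whichever sensitivity method is more conservative leaves the favoured result undefined

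*Combined protocol and SAP*

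**What the plan says.** Section 11.3.2 (Analysis Plan) sets the premise: "missing data are expected to be MNAR as patients with poor QOL tend to have lower chances of completing a questionnaire", and adds that this applies particularly shortly before death. The primary analysis follows from it: a pattern-mixture model on the repeated FACT scores, stratified by survival, estimates the change from baseline to week 12.

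The same section then covers robustness: "Sensitivity analysis will be conducted by exploring imputation method such as the last-observation carried forward". Worst-rank score analysis is the other method named, and the sentence ends with "favoring the more conservative method". The plan does not define conservative, does not rank the two methods, and does not say what is reported if they disagree.

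Three other places bear on the point:

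- The table in Section 6.2 schedules the FACT at baseline and weeks 6, 12 and 24. Only a baseline or week-6 score can be carried forward to week 12.
- Section 6.2 also drops the questionnaire requirement once a patient is in hospice.
- Section 1.3 (Aim 2) hypothesises more hospice use with early palliative care (PC) than with standard care (SC).

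**The concern.** A sensitivity analysis should show whether a positive primary result survives plausible departures from the primary model's assumption. A pattern-mixture model stratified by survival estimates each stratum from the forms that were returned. The untestable step is that non-completers in a stratum resemble those who did respond. The departure to test is that they did worse.

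LOCF does not pose that question. A patient with no week-6 form is scored as zero change, and a patient with one is scored as having stopped declining at week 6. Any further decline is removed from the comparison.

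This matters for the arm contrast when missing rates or declines differ by arm. The hospice exemption, combined with the hypothesis of more hospice use under early PC, makes an excess of missing forms in the PC arm plausible, although the documents give no rate by arm. In that case LOCF would hide a disadvantage for PC and make a favourable result look sturdier than it is.

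The preference clause does not repair this. Neither named method is conservative in advance: LOCF can err in either direction, and worst-rank favours whichever arm has fewer deaths or missing forms.

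**Working it through.** **1. The plan's own figures (Section 11.2.1).** Inputs: "at least a 4-point change from baseline to week 12"; "standard deviation was 11.87 from the pilot study"; "two-sided two-sample *t*-test with at 5% significance level"; 1:1 allocation (Section 1.4).

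n per arm = 2 × (1.960 + 0.842)² × 11.87² / 4² ≈ 138.2, rounded up to 139. The plan states 140, so the figure reproduces. Power at 140 per arm is 80.5% by the normal formula and 80.2% by the noncentral t. Inflation for 30% missing gives 140 / 0.70 = 200 per arm. With 200 per arm, 20–30% missing leaves 160–140 evaluable, with power of about 85–80%. The present point disputes none of this.

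**2. Formula for the LOCF bias.** Let m be the proportion missing week 12 in an arm, d the true mean change of those missing, and c the share of that change which LOCF carries forward. Completers contribute the same under LOCF as in truth, so

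bias in (PC − SC) = (1 − c) × (m_SC × d_SC − m_PC × d_PC).

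**3. Direction.** Missing rates use the two ends of the plan's 20–30%. The declines, and c = 0 or 0.5, are assumptions.

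| Missing SC / PC | True change of missing, SC / PC | Bias, c = 0 | Bias, c = 0.5 |
|---|---|---|---|
| equal (20–30%) | −12 / −12 | 0 | 0 |
| 20% / 30% | −12 / −12 | +1.2 | +0.6 |
| 30% / 20% | −12 / −12 | −1.2 | −0.6 |
| 20% / 20% | −12 / −8 | −0.8 | −0.4 |
| 30% / 30% | −12 / −8 | −1.2 | −0.6 |
| 20% / 30% | −12 / −8 | 0 | 0 |
| 30% / 20% | −12 / −8 | −2.0 | −1.0 |

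Positive values favour PC. The range is −2.0 to +1.2 points, and the sign depends on arm-specific quantities unknown before the data are in.

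**4. Size when one arm has more missing data.** Assume 30% versus 20% missing, completers with zero mean change in both arms, and missing patients in both arms falling D = 10 to 20 points more. The true contribution to the arm difference is 0.10 × D = 1.0 to 2.0 points, against the arm with more missing data.

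Assume half of the missing patients have a week-6 score, and let f be the fraction of the decline already visible then. So c = 0.5 × f, and the share hidden is 1 − 0.5f.

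| f | Share hidden | Points hidden, D = 10 | Points hidden, D = 20 |
|---|---|---|---|
| 1 | 50% | 0.5 | 1.0 |
| 0.5 | 75% | 0.75 | 1.5 |
| 0.25 | 87.5% | 0.875 | 1.75 |
| 0 | 100% | 1.0 | 2.0 |

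The hidden amount is 0.5 to 2.0 points, or 12.5% to 50% of the 4-point target.

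**5. The preference clause.** This was examined in a simulation under no arm effect, with assumed inputs: 200 per arm, SD of week-12 change 11.87, about 28% missing with probability rising as the week-12 score falls, half of the missing with a week-6 score, 4,000 runs.

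| Rule | Rejects at 5% |
|---|---|
| LOCF alone | 5.1% |
| Worst-rank alone | 4.9% |
| Larger of the two p-values | 1.3% |
| Smaller of the two p-values | 8.6% |

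The two methods disagreed on significance in 7.3% of runs. Which one counts as more conservative is therefore a real question in some trials, and it is answered only by the results.

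**The case against.** The strongest reply is that the plan already takes informative missingness seriously. The primary model is built for it, and worst-rank analysis, the other named method, is designed for informatively missing observations. A sensitivity analysis is also meant to rest on a different assumption from the primary one. All of this stands. A reader might infer that the plan contradicts itself, or that it has no protection against informative missingness; the documents support neither. What remains is that LOCF varies the assumption in an unhelpful direction, because it removes the expected decline rather than enlarging it.

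A reader might also infer that choosing a method after the results inflates type I error. If conservative means the less favourable result, it does not: that rule rejected 1.3% in the simulation. The 8.6% belongs to the opposite rule, which the plan does not propose. Neither the primary test nor the gatekeeping in Section 11.4.2 is stated to depend on the choice, and nothing says that only one sensitivity result will be reported.

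Third, it is tempting to say that LOCF flatters PC, or to attach one hidden share such as 87.5%. The documents support neither. With more missing data in SC and equal declines the bias runs against PC, and the hidden share depends on how much decline is visible by week 6, which the documents do not give. Missing rates above 30% would also lie outside the plan's stated range.

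**Conclusion.** The point holds as a weakness in the robustness check. LOCF freezes the patients whom the plan expects to be worsening, does not stress the primary model's assumption, and cannot be relied on to be conservative. Its bias is about zero with equal missing rates and equal declines. With a 10-percentage-point gap in missing rates and 10 to 20 points of excess decline it hides 0.5 to 2.0 points of a 1.0 to 2.0 point contribution. Those figures rest on the assumed decline, the assumed half with a week-6 score and zero mean change in completers; only the 20% and 30% missing rates and the 4-point target come from the plan. A PC excess of missing forms is plausible from Sections 6.2 and 1.3 but is not quantified there.

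The clause "favoring the more conservative method" leaves unclear which result is favoured. That is a gap in pre-specification, not an error-rate problem. The primary test, the 200 per arm and the 5% level are unaffected.

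**What to change.** In Section 11.3.2:

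- Replace LOCF with a delta-adjusted (tipping-point) pattern-mixture analysis. Lower the imputed week-12 FACT-G scores by shifts varied separately in each arm over a pre-specified range, for example 0 to 20 points. That grid is an assumption and should be settled by the study team. Report the shift, or pair of shifts, at which the conclusion changes.
- Keep the worst-rank analysis.
- State that both analyses will be reported whatever they show.
- Delete "favoring the more conservative method".

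The cost is SAP wording and modest programming. Sample size, data collection and patient care do not change.

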9.0 MEASURES

Demographics: All study participants will complete a demographic questionnaire (see Appendix III for patient, Appendix IV for family caregiver) at the time of baseline data collection detailing their age, sex, race, ethnicity, religion, relationship status, education level, annual household income, and living situation (specify number of dependent children living at home). Family caregivers will also specify their relationship with the patient, living situation (specify number of dependent children living at home) and employment status.

QOL-Patient: To assess quality of life over time in study patients, we will use the Functional Assessment of Cancer Therapy (FACT) Questionnaires, which have been validated for use in multiple care settings and with diverse tumor types. The FACT consists of four subscales assessing well-being across four domains (physical, functional, emotional and social) during the prior seven days. Additional questions specific to cancer symptoms will be added to the measure for each tumor type, including lung (FACT-L), esophageal and gastric (FACT-E), and hepatic, biliary, and pancreatic (FACT-Hep) – See Appendix III.⁵⁸⁻⁶¹ Patients will complete this questionnaire at baseline, 6, 12 and 24 weeks.

QOL-Family caregiver: We will use short-form health survey (SF-36) to assess change in health-related QOL over time in family caregivers (see Appendix IV).⁶² The SF-36 measures eight domains of health-related quality-of-life: physical functioning, role limitations due to physical health, bodily pain, general health perceptions, vitality, social functioning, role limitations due to emotional health, and mental health. Family caregivers will complete this questionnaire at baseline, 6, 12 and 24 weeks.

Mood: We will use the Hospital Anxiety and Depression Scale (HADS) to assess symptoms of depression and anxiety in all study participants (see Appendix III for patient, Appendix IV for family caregiver).⁶³ The HADS is a 14-item questionnaire that contains two 7-item subscales assessing depression and anxiety symptoms during the past week. Scores on each subscale range from 0 to 21, with a cutoff of 8 or greater denoting clinically significant depression or anxiety symptoms. Patients and family caregivers will complete questionnaire at baseline, 6, 12 and 24 weeks.

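### The primary model in section 11.3.2 commits to no adjustment for baseline FACT-G and leaves the minimization factors optional; fixing both in advance can gain precision and needs no new data.

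*Combined protocol and SAP*

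**What the plan says.** Section 11.3.1 defines the endpoint: "Change in FACT-G scores from baseline to 12 weeks between study arms will be the primary endpoint for this study". Section 11.3.2 analyses it with a pattern mixture model, in which "repeated measures of FACT will all be included in the repeated measures model to estimate the change from baseline to 12 weeks". FACT is given at four visits (section 9.0: "Patients will complete this questionnaire at baseline, 6, 12 and 24 weeks"), so baseline is one of the outcomes. No baseline covariate is named, and nothing says that the arms share a baseline mean.

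The pattern mixture model is meant "to adjust for MNAR bias by stratification based on survival data". The arms are then compared by "weighting the within-stratum estimates with the estimated probability of being in each distinct combination of intervention arm and survival duration".

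On other covariates the text is permissive: "Selected demographic and clinical factors (including stratification factors) may be incorporated when examining change in QOL scores across the four time points". The selected factors are not listed. Tumor type (three levels) and family caregiver participation (yes/no) drive the Pocock-Simon allocation in sections 1.4, 4.6 and 4.7, but no section commits to having either in the primary model.

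**The concern.** When baseline is an outcome with its own mean in each arm, the model estimates the week-12 difference as a difference in changes. Chance imbalance at baseline is then subtracted in full. Regression on baseline subtracts only the part that predicts week 12. With complete data the free-means model has exactly the precision of the change score. With incomplete data it also draws on partial records, but it still does not use the baseline efficiently.

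Three things are at stake. The first is precision in the primary test. The second is the gatekeeping sequence in section 11.4.2, where the caregiver and end-of-life analyses are formally tested only if the preceding analysis is significant. The third is that an optional, unlisted covariate set leaves open a choice that could be made after the data are seen.

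**Working it through.** **Inputs from the documents.** Section 11.2.1 gives a difference of 4 points, two-sided 5%, 140 complete per arm and 200 enrolled per arm. It also says "standard deviation was 11.87 from the pilot study", and that "the rate of missing data for primary endpoint patient-reported measures was approximately 20-30" percent.

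**Assumptions.** The SD of 11.87 is the SD of change, as the t-test implies. The correlation ρ between baseline and week 12 is not given, so 0.5, 0.7 and 0.8 are shown. SDs at the two visits are equal unless stated otherwise.

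**1. The plan's own figure.** A two-sample t-test with difference 4 and SD 11.87 needs 139.2 per arm, so 140, and has 80.2% power at 140. Also 140/(1 − 0.30) = 200. The sample size reproduces.

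**2. Complete data.** With common SD σ, Var(change) = 2σ²(1 − ρ) and Var(week 12 given baseline) = σ²(1 − ρ²). The ratio is (1 + ρ)/2, so the adjusted SD is 11.87·√((1 + ρ)/2).

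| ρ | Adjusted SD | Power at 140 per arm (80.2% unadjusted) |
|---|---|---|
| 0.5 | 10.28 | 90.0% |
| 0.7 | 10.94 | 86.2% |
| 0.8 | 11.26 | 84.2% |

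**3. 200 per arm, all visits used, no survival strata.** Expected information, exchangeable correlation, monotone dropout completely at random: 15/30/45% missing at weeks 6/12/24, or 10/20/35%.

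| Missing at week 12 | ρ | Free baseline means | Adjusted |
|---|---|---|---|
| 30% | 0.5 | 84.0% | 90.8% |
| 30% | 0.7 | 83.3% | 87.4% |
| 30% | 0.8 | 82.9% | 85.7% |
| 20% | 0.5 | 87.4% | 93.8% |
| 20% | 0.7 | 87.0% | 91.0% |
| 20% | 0.8 | 86.8% | 89.5% |

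The variance ratios at 30% missing are 0.808/0.887/0.925.

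**4. Unequal SDs.** If the week-12 SD is k times the baseline SD, the complete-data variance ratio is k²(1 − ρ²)/(1 + k² − 2kρ). At k = 1.25 and ρ = 0.8 this is 0.5625/0.5625 = 1: the slope kρ equals 1 and adjustment gains nothing. With 30% missing and k = 1.25, power goes from 82.4/81.9/81.9% to 85.4/82.4/81.9%. With k = 1.10 (week-6 SD midway) it goes from 82.5% to 84.7% at ρ = 0.7 and from 82.2% to 83.1% at ρ = 0.8.

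**5. With survival strata (illustration; all settings assumed).** 200 per arm; 25% short survivors, 4 and 8 points lower at weeks 6 and 12; stratum related to baseline (latent correlation 0.4); about 30% missing at week 12, dependent on the last score; arm-specific weights; 8,000 runs. Power goes from 82.0/80.4/81.1% to 86.6/83.0/81.7% (variance ratios 0.880/0.935/0.983).

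**6. Does the covariate bias the stratified estimate?** With observed arm-specific stratum proportions as weights and a common slope b, the adjusted contrast minus the free-means contrast equals (1 − b) × the arm difference in mean baseline over all patients. That term has mean zero when the arms are comparable at baseline. As a test, short survival was set to 32% in one arm and 18% in the other, so the true difference is 4 + 8 × 0.14 = 5.12.

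| Model | Mean estimate at ρ = 0.5/0.7/0.8 |
|---|---|
| Free baseline means | 5.13/5.14/5.13 |
| Baseline as covariate | 5.14/5.13/5.13 |
| Common baseline mean within strata | 4.59/4.71/4.79 |

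The third model is biased by −0.53/−0.41/−0.33, because survival strata are formed after randomization and the arms need not share a baseline mean within them.

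**7. Minimization factors alone.** SD = 11.87·√(1 − R²). For assumed R² of 2/5/10%, power at 140 complete per arm is 81.0/82.2/84.2%.

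**The case against.** The strongest objection is that the large gains do not belong to the planned analysis. They come from unstratified models with equal SDs at both visits. The protocol itself expects symptom burden to intensify near the end of life, so a wider spread at week 12 is plausible, and even a 10% larger SD cuts the gain sharply. In the stratified illustration the gain is 4.6, 2.6 and 0.6 points. This stands: the size is uncertain and may be nil.

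The plan is also silent on baseline means; it does not say they are free by arm. True, but a primary model that leaves this unstated is under-specified.

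The sentence on optional factors could refer only to the four-visit description, which is a secondary endpoint in section 11.4.1.1. That reading is possible. However, the sentence follows directly on the primary model, and no other text commits to the factors.

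A common slope across survival strata is a restriction. A separate stratified check with slopes that differed by stratum gave nearly the same mean for the adjusted and free-means contrasts, so this does not defeat the proposal.

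A patient without a baseline FACT would leave a model that uses baseline as a covariate. Such patients should be few, because sections 7.1.1 and 7.2.1 place the questionnaire on the day of registration. The survival cut-points are also undefined, but that is a separate matter.

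**Conclusion.** The concern holds as a recommended improvement, with medium confidence. The primary model commits to neither baseline adjustment nor the minimization factors, although both are available. It is not an error of validity or of sample size: the stated 80% power is met without adjustment.

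With equal SDs and no survival strata, adjustment at 200 per arm is worth about 3 to 7 power points for ρ between 0.5 and 0.8. It is worth less under stratification and can be worth nothing if variability grows by week 12. These sizes rest on assumed values of ρ, SD ratio and dropout pattern; the gain for the planned estimate cannot be computed from the documents. The gain from the two factors alone may be small. Closing the open covariate choice is worthwhile whatever the gain in precision.

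**What to change.** In section 11.3.2, replace the sentence that puts all FACT measures in the model and the sentence on optional factors with:

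> Within the pattern mixture analysis, FACT-G at weeks 6, 12 and 24 are the outcomes of the repeated measures model. Baseline FACT-G (centred at the overall mean of all evaluable patients) and its interaction with visit, with slopes common to arms and survival strata, tumor type (3 levels) and caregiver participation (yes/no) are fixed covariates, with arm by visit within each survival stratum. Survival strata and weights are as stated above, the weights being estimated from all evaluable patients in each arm. The weighted week-12 arm difference, adjusted for baseline, is the primary contrast. Any other covariate is a sensitivity analysis.

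Baseline has to leave the outcome list. If it stays there and is also a covariate with one slope under unstructured covariance, the slope goes to 1 and the contrast returns to the raw change difference. A common baseline mean should not be imposed within survival strata, for the reason shown in step 6.

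The endpoint in section 11.3.1 is unchanged: conditional on baseline, the arm difference in week-12 score and in change is the same number. The cost is one model specification, settled before the data are analysed. No patients, visits or data items are added, since sections 4.6, 4.7, 6.2 and 9.0 already provide for baseline FACT and both factors.
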